## **10.2 General Study Procedures**

A signed and dated IRB-approved informed consent must be obtained before any study-specific procedures are performed. Procedures that are part of routine care are not considered study-specific procedures and may be used at screening to determine eligibility. All subjects will be screened for eligibility before enrollment. Only eligible subjects will be enrolled into the study.

### **10.2.1 Informed Consent**

A signed informed consent must be obtained from each subject prior to any study mandated procedures.

### **10.2.2 Medical History**

The investigator or designee will collect a complete medical and surgical history prior to enrollment. Medical history will include information on the subject's concurrent medical health conditions, relevant past medical conditions, and surgical history.

Relevant medical history, including antecedent hematologic or oncologic disease, other diseases/symptoms such as fatigue, bleeding and infection (resolved and ongoing) will be collected. The current toxicity grade will be collected for each condition that has not resolved.

### **10.2.3 Prior Therapy**

The investigator or designee will collect relevant prior therapy which includes previous chemotherapy or radiotherapy and anticancer therapies (eg, stem cell transplant).

### **10.2.4 Physical Examinations**

A complete physical examination will be performed by the investigator or designee according to local practices at screening and time points specified in the Schedule of Assessments ([Table 6](#)). The physical exam will include a neurological assessment.

### **10.2.5 Peripheral Neuropathy Assessment**

The peripheral neuropathy assessment should be done at screening and time points specified in the Schedule of Assessments ([Table 6](#)). All assessments must be reported on the corresponding eCRF page (see [Appendix G](#) for peripheral neuropathy assessment tool).

### **10.2.6 Height Measurements**

Height (cm) will be measured without shoes at screening.

#### **10.2.7 Weight Measurements**

Weight (kg) without shoes will be obtained at screening and time points specified in the Schedule of Assessments ([Table 6](#)).

#### **10.2.8 Vital Signs**

The following measurements must be performed: systolic/diastolic blood pressure (BP), respiratory rate, heart rate and temperature. Subject must be in rested and calm state for at least 5 minutes before BP assessments are conducted. The position selected for a subject should be the same that is used throughout the study and documented on the vital sign eCRF. Record all measurements on the vital signs eCRF.

The temperature location selected for a subject should be the same that is used throughout the study and documented on the vital signs/temperature eCRF. Vital signs will be recorded by the investigator or designated site physician at screening and time points specified in the Schedule of Assessments (see [Table 6](#)).

Abnormal measurements may be repeated at the discretion of the investigator and must be reported on the corresponding eCRF page. When vital signs and blood sample collection occur at the same time, vital signs should be performed before blood samples are drawn.

#### **10.2.9 Eastern Cooperative Oncology Group Performance Status**

Eastern Cooperative Oncology Group Performance Status ([Appendix E](#)) assessments will occur at time points specified in the Schedule of Assessments (see [Table 6](#)).

#### **10.2.10 Electrocardiogram**

Subject must be in a supine position in a rested and calm state for at least 5 minutes before ECG assessment is conducted. If the subject is unable to be in the supine position, the subject should be in the most recumbent position as possible.

ECGs should be performed in accordance with the Schedule of Assessments (see [Table 6](#)), in triplicate, in a standardized method, prior to blood draws or other invasive procedures. Each ECG must include the following measurements: QRS, QT, QTc, RR, and PR intervals.

Electrocardiograms will be performed as follows:

- Triplicate ECGs will be performed at screening approximately 30 seconds apart and run consecutively, the interval between tracings should not be greater than 60 seconds
- All other ECGs will be performed in triplicate (approximately 30 seconds apart and run consecutively, the interval between tracings should not be greater than 60 seconds)
- After cycle 2, ECGs are only required if oprozomib dose is less than 270 mg and it is clinically indicated. If interval prolongation > 480 msec occurs (and is a 30 msec increase above baseline), subject's serum potassium, magnesium, calcium and phosphorus should be measured immediately and replaced if needed
- All subjects receiving 270 mg or higher of oprozomib (IR tablet only) in combination with pomalidomide and dexamethasone will require triplicate ECGs 1 and 2 hours after oprozomib dose on C1D8 and C2D1.

When ECGs, vital signs, blood for laboratory tests and PK are to be collected at the same time points, the ECGs and vital signs will be collected prior to blood collections.

The principal investigator or designated site physician will review all ECGs. Once signed, the original ECG tracing will be retained with the subject's source documents. At the request of the sponsor, a copy of the original ECG will be made available to Amgen.

Findings will be recorded on the ECG eCRF.

#### **10.2.11 Echocardiogram (ECHO) / Multigated Acquisition (MUGA) Scan**

ECHO or MUGA will be performed to assess cardiac ejection fraction and cardiac valve abnormalities and will occur at screening only. The test can be repeated if clinically indicated by the investigator.

#### **10.2.12 Tumor Assessments**

##### **10.2.12.1 Serum Protein Electrophoresis (SPEP) and 24-hour Urine Protein Electrophoresis (UPEP)**

Serum protein electrophoresis (SPEP) and 24-hour urine protein electrophoresis (UPEP) are required for all subjects at screening. Thereafter, SPEP and UPEP with 24-hour urine collection are to be done at each time point for all subjects as indicated in the Schedule of Assessments.

##### **10.2.12.2 Immunofixation**

Immunofixation is done at screening and is required at next assessment only if SPEP or UPEP results are zero or undetectable.

#### **10.2.12.3      Bone marrow**

Bone marrow sample will be collected from all subjects during screening to quantify percent myeloma involvement and for fluorescent in situ hybridization (FISH); FISH will be performed locally. An additional bone marrow sample will only be required to confirm a complete response (CR).

#### **10.2.12.4      Serum Free Light Chain**

Serum free light chain (sFLC) assay and ratio will be performed at each time point as specified in the Schedule of Assessments ([Table 6](#)).

#### **10.2.12.5      Quantitative Immunoglobulin**

Quantitative immunoglobulin (Ig) will be performed at screening. Quantitative immunoglobulin will be repeated only if clinically indicated, ie, frequent infection despite multiple myeloma disease control or when deemed clinically indicated by the investigator.

#### **10.2.12.6      Beta-2 Microglobulin**

Beta-2 microglobulin will be performed only at baseline as part of risk stratification.

### **10.2.13      Imaging Assessments**

#### **10.2.13.1      Bone Lesion Assessment**

A skeletal survey, low-dose CT scan or bone marrow MRI should be performed during screening. The same methodology will be repeated as clinically required as described in the Schedule of Assessments ([Table 6](#)). Skeletal survey is defined by X-rays of lateral view of the skull, anteroposterior and lateral views of the spine and anteroposterior views of the pelvis, ribs, femora, and humeri. Subjects with bone pain that have a normal skeletal survey should have a MRI.

#### **10.2.13.2      Plasmacytoma Assessment**

A plasmacytoma survey will be performed at the time points as specified in the Schedule of Assessments ([Table 6](#)). For subjects without a history of extramedullary disease, assessment by physical examination at screening is acceptable. Plasmacytoma evaluation is to be repeated during treatment only to confirm a response of PR or better, to confirm PD, or if clinically indicated. If clinically indicated due to history of extramedullary disease, the same technique (may include ultrasound, x-ray, CT scan, MRI, PET, or other standard-of-care method) must be employed for each measurement.

#### 10.2.14 Pharmacokinetic Blood Sampling

Blood samples for quantitative determination of plasma concentrations of oprozomib and its [REDACTED], will be collected at time points specified in the Schedule of Assessments ([Table 6](#)). The time points are:

C1D1: pre-dose, 1-3 hours post-dose and 4-6 hours post-dose

C1D8: pre-dose, 0.5 hours post-dose, 1 hour post-dose, 2 hours post-dose, 4 hours post-dose, 6 hours post-dose, 8 hours post-dose (for the GR formulation only)

C1D9: pre-dose (for the GR formulation only)

C1D22: pre-dose, 0.5 hours post-dose, 1 hour post-dose, 2 hours post-dose, 4 hours post-dose, 6 hours post-dose

C1D23: pre-dose (for the GR formulation only)

C3D1: pre-dose, 1-3 hours post-dose, 4-6 hours post-dose

C5D1: pre-dose, 1-3 hours post-dose, 4-6 hours post-dose.

On PK collection days, the time of meal intake will be recorded on the eCRF. PK samples should be collected at the exact nominal time point as noted. The permitted time windows for PK post-dose collection on C1D8 and C1D22 are:  $\pm$  5 minutes for the 0.5 and 1 hour time points,  $\pm$  10 minutes for the 2 hour time point and  $\pm$  20 minutes thereafter. The C1D8 8 hour post-dose and the C1D9 and C1D23 pre-dose PK collections will occur only for the GR formulation. Sample collection, processing, storage, and shipping instructions are provided in a separate laboratory manual.

#### 10.2.15 Blood Samples

Approximate blood volumes expected to be collected during study participation are presented in [Table 7](#).

**Table 7. Approximate Blood Collection Volumes**

Test	Volume (mL) per Collection	Approximate Number of Collection	Approximate Total Volume (mL)
Laboratory safety (chemistry, hematology, coagulation)	15 mL	19	285mL
Serology	5 mL	13	65 mL
Quantitative Immunoglobulin	10 mL	1	10 mL
Serum pregnancy test (females of child bearing potential only)	3 mL	16	48 mL
Blood samples for oprozomib PK	3 mL	4	72 mL
[REDACTED]			
Total blood volume assumes 10 cycles for study participation plus screening and EOS (if applicable)			~520 mL

#### **10.2.16 Clinical Laboratory Assessments**

Blood samples for clinical chemistry, hematology, and urine samples for urinalysis, will be collected at screening, and at time points specified in the Schedule of Assessments (Table 6). All tests (except for PK and [REDACTED]) are to be performed at a local laboratory and test results are to be recorded in the eCRF. Blood samples will be obtained by venipuncture before study drug administration. All laboratory tests must be reviewed by the investigator or qualified designee. Additional safety laboratory assessments may be performed if clinically indicated at the discretion of the investigator. The following tests listed in Table 8 will be conducted on samples collected by standard laboratory procedures.

**Table 8. List of Analytes**

Chemistry	Hematology	Urinalysis	Coagulation
Albumin	ANC	Blood	PT
ALP	Hematocrit	Protein	PTT
ALT	Hemoglobin	Ketones	INR
Amylase	Platelets	Bilirubin	
AST	RBCs	Glucose	Other Labs:
Bicarbonate	WBCs	Leucocytes esterase (WBC)	Pregnancy
BUN or Urea	Differential: 

▪ Neutrophils

▪ Lymphocytes

▪ Monocytes

▪ Eosinophils

▪ Basophils

	Microscopic exam (only needed for positive dipstick and should include the following): Epithelial, Bacteria, Casts, Crystal, RBCs, WBCs	Hep B surface antigen Hep B antibody Hep C antibody HCV PCR (if applicable) HBV PCR (if applicable) PK
Calcium			
Chloride			
Creatinine			
Direct bilirubin			
Glucose			
LDH			
Lipase			SPEP
Magnesium			UPEP
Phosphorus			sFLC
Potassium			Quantitative immunoglobulin
Sodium			Beta-2 microglobulin
Total bilirubin			Immunofixation
Total protein			
Uric acid			

Additional procedures deemed necessary as part of standard of care or as required by local laws and regulations may be performed at the investigator's discretion.

#### **10.2.17 Screening**

After obtaining informed consent, all screening procedures and tests establishing eligibility will be performed within a period of 28 days before dosing and 14 days for laboratory assessments. If acceptable screening laboratory assessments are within 48 hours of study day 1, the pre-dose laboratory assessments do not need to be obtained. The following procedures are to be completed during the screening period at time points designated in the Schedule of Assessments ([Table 6](#)).

#### **10.2.18 Screening Procedures to Determine Eligibility**

- Confirmation that the Informed Consent Form has been signed and dated
- Review of inclusion and exclusion criteria to determine eligibility
- Demographic data including sex, age, race, and ethnicity will be collected in order to study their possible association with subject safety and treatment effectiveness.

- Review of medical and surgical history including:
  - concomitant medication
  - documentation of diagnosis including history of current and prior cancers
  - prior anticancer treatments
- Clinical evaluation which includes the following:
  - physical examination with neurological assessment, ECOG performance status, height and weight
  - assessment according to CTCAE version 4.03 for prior and continuing diagnosis, disease complications and toxicities
- Peripheral neuropathy assessment
- Vital signs (blood pressure, respiratory rate, heart rate, temperature)
- 12-lead ECG in triplicate
  - collected in the supine position after subject has rested for 5 minutes
  - record QRS, QT, QTc, RR and PR intervals
- ECHO or MUGA
- Safety laboratory assessments (locally tested) within 14 days of study day 1
  - Chemistry
  - Hematology
  - Coagulation
  - Urinalysis
- Serum pregnancy test (only for females of childbearing-potential)
- Determination of HIV status (via medical history)
- Hepatitis serology
  - HBsAg and total HBc
    - If results are HBc positive and HBsAg positive, no additional testing is necessary
    - If results are HBc positive and HBsAg negative, additional testing for hepatitis B virus DNA by PCR is necessary
  - HepCAb
    - If results are HepCAb positive, additional testing for hepatitis C virus RNA by PCR is necessary.
- Disease assessments
  - Serum protein electrophoresis (SPEP)
  - 24-hour urine protein electrophoresis (UPEP)
  - Immunofixation
  - Serum free light chain (sFLC)
  - Quantitative immunoglobulin
  - Beta-2 microglobulin
  - Bone marrow aspirate

- [REDACTED]
- Imaging assessments
  - Plasmacytoma
  - Bone lesions
- Adverse event assessment is performed throughout the study at every visit
  - Serious adverse events are collected from the time the subject signs the informed consent form
  - Adverse events are collected from the time the subject is dosed on day 1

Subjects can be rescreened at the discretion of the investigator after consultation with Amgen. The investigator must provide appropriate rationale prior to repeating any screening procedures or tests during the screening period. A new consent must be signed unless it has been > 28 days since the last consent was signed.

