## 8. SUBJECT ENROLLMENT

Before subjects begin participation in any study-specific procedures, Amgen requires a copy of the site's written institutional review board/independent ethics committee (IRB/IEC) approval of the protocol, informed consent form, and all other subject information and/or recruitment material (see Section [14.2](#)).

All subjects must personally sign and date the IRB/IEC approved informed consent form (ICF) before commencement of study-specific procedures. Each subject who signs the informed consent enters into the screening period for the study and receives a unique subject identification number before any study procedures are performed. The subject identification number will be assigned manually. This number will be used to identify the subject throughout the clinical study and must be used on all study documentation related to that subject.

The unique study identification number will consist of 11 digits. The first 3 digits will represent the last 3 digits of the protocol number (eg, 104). The next 5 digits will represent the country code and site number (eg, 66001) and will be identical for all subjects at the site. The next 3 digits will be assigned in sequential order as subjects are screened (eg, 001, 002, 003). For example, the first subject to enter screening at site 66001 will receive the number 10466001001, and the second subject at the same site will be 10466001002. The subject identification number must remain constant throughout the entire clinical study; it must not be changed after initial assignment, including if a subject is rescreened.

All screening tests and procedures should be performed within 28 days prior to study day 1, unless otherwise indicated. All blood and urine samples collected for screening assessments will be submitted and analyzed by the local laboratory. Time permitting, screening laboratory assessments used to determine subject eligibility may be repeated once (up to a total of 2 times during the 28 day screening period), if necessary.

Subjects who do not meet eligibility criteria within the 28 day screening period will not be eligible for enrollment. Subjects may be re-screened up to 2 additional times at the

---

discretion of the investigator. The subject must be re-consented if a re-screening attempt occurs outside of the 28 day screening period. Subjects who are deemed ineligible will be documented as screen failures.

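### Protocol section 10.2.18 states the re-consent rule for re-screened subjects in reverse: it waives a new signature after 28 days, where section 8 requires one

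*Protocol*

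**What the plan says.** Two places in the current body of the protocol tell sites when a re-screened subject must sign again.

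- Section 8 (Subject Enrollment): "The subject must be re-consented if a re-screening attempt occurs outside of the 28 day screening period". The same section allows up to two further screening attempts per subject. It fixes the start of the period, "Each subject who signs the informed consent enters into the screening period for the study", and its length, "Subjects who do not meet eligibility criteria within the 28 day screening period will not be eligible for enrollment".
- Section 10.2.18 (Screening Procedures to Determine Eligibility): the closing paragraph opens with "Subjects can be rescreened at the discretion of the investigator after consultation with Amgen" and ends with "A new consent must be signed unless it has been > 28 days since the last consent was signed".

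Neither sentence sits in an amendment summary, a redacted area or a broken table. The SAP does not mention re-consent, and no other section of the protocol settles which sentence governs.

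**The concern.** The exception in 10.2.18 points the wrong way. A time limit on consent is normally there so that a subject who comes back after a long gap signs again. As worded, 10.2.18 excuses exactly that subject and asks for a fresh signature from the one who signed recently.

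This is an operating instruction, placed in the section that staff are likely to have open when they re-screen someone. That section's list begins with checking that the consent form has been signed. The general requirement in sections 8, 10.2 and 10.2.1 for consent before study procedures may not catch the omission, because the subject's previous signature arguably meets it. The specific re-consent rule therefore has to do the work. What is at stake is a missed re-consent and the protocol deviation that follows under section 8. No trial result is at stake.

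**Working it through.** No sample size, power or error-rate figure is involved, so there is no arithmetic to reproduce. The check is a comparison of the two rules.

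**Step 1: do the two 28-day limits refer to the same clock?** Section 10.2.18 counts days since the last consent. Section 8 refers to the screening period, which it says a subject enters on signing the consent and which lasts 28 days. On that definition, falling outside the period and being more than 28 days from consent are the same condition.

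**Step 2: apply each rule on both sides of day 28.**

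| Days since last consent | Section 8 | Section 10.2.18 as written |
|---|---|---|
| 28 or fewer | no new signature called for | new signature required |
| more than 28 | new signature required | requirement waived |

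The rules differ in both rows. This is a reversal and not a difference in strictness.

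**Step 3: does another reading of the period remove the conflict?** Sections 8 and 10.2.17 also describe the 28 days as counted back from study day 1 or first dosing. Under that reading the boundary may fall on a different calendar day. The direction does not change: section 8 still asks for a new consent at the later attempt, and 10.2.18 still lifts the requirement as the consent ages.

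**Step 4: test the correction.** With *if* in place of *unless*, 10.2.18 requires a new signature beyond 28 days and none at 28 days or fewer. Both rows of the table then agree with section 8. Keeping *unless* and changing the limit to 28 days or fewer gives the same result.

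**The case against.** The best case on the other side is that this is an obvious drafting slip with little practical reach. Four parts of it stand.

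- **The rules can be obeyed together.** Beyond 28 days, 10.2.18 drops a requirement but does not forbid signing. A site that obtains a signature whenever either section asks for one complies with both. Section 8 is equally binding and states the rule clearly. A reader might infer that sites *would* enrol subjects on an out-of-date consent. The documents support only that a site relying on 10.2.18 alone *could* do so.
- **Only one side of day 28 loses a protection.** Within 28 days, 10.2.18 merely asks for an extra signature. It would be wrong to count every re-screened subject as exposed.
- **No consequence for the data is documented.** A reader might infer that affected data would become inadmissible. Nothing in the protocol or SAP links the timing of re-consent to excluding data. Nor do the documents show that an older consent would lack newer risk information. Sections 14.1 and 14.2 handle changes to the consent form separately, although they give no re-consent rule of their own.
- **Little screening may remain.** Section 6.5.2 places the primary analysis after target enrolment has been reached, and section 5.5.5 already reports primary-analysis-period results for a study with 54 subjects enrolled. The documents do not expressly say that screening has closed, so this is an inference.

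None of this makes the sentence in 10.2.18 correct or consistent with section 8.

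**Conclusion.** Wrong as written: an internal inconsistency of low severity. Section 10.2.18 reverses the re-consent rule in section 8, and the two sections disagree whether the last consent is more or less than 28 days old. The subjects who could lose a protection are those re-screened more than 28 days after their last consent at a site that did not apply section 8. Their number is not given and cannot be estimated from the documents. Every re-screened subject has already signed at least one consent, so this is not a question of treatment without consent. No estimate, error rate, sample size or analysis set changes.

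The conclusion assumes that section 8 expresses the intended rule, which is the only direction in which a 28-day limit on consent serves a purpose. That the two clocks coincide rests on section 8's statement that screening begins at signature. The reversal itself does not depend on it.

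**What to change.** Either replace *unless* with *if* in the last sentence of 10.2.18, or delete that sentence and refer to section 8. The cross-reference is cleaner: it leaves a single rule and avoids keeping two descriptions of the 28-day limit, one counted from signature and the other tied to the screening period.

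The cost is one word or one sentence at the next amendment, with no change to dosing, visits, data collection or the SAP. If screening has already closed, the useful remaining step is to list any re-screened subjects, compare their consent dates with the dates of re-screening, and record as a deviation from section 8 any who passed 28 days without signing again.
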